7.5 SECONDARY ENDPOINTS

Event-free survival (EFS)

EFS will be analyzed with the Kaplan-Meier method for each of the treatment arms as well as overall treatments. An exploratory (non-stratified) logrank test will be used to compare the different treatment arms. For phase II Kaplan-Meier curves for EFS in the genetic subgroups defined in [Section 6.4](#) will be presented separately.

The percentage of patients who are event free will be displayed at monthly or greater time intervals as appropriate.

Patients for whom no leukemia assessment is available within 42 days prior to discontinuation from treatment will be examined on a case by case basis. A listing will be provided.

Overall survival

Overall survival will be analyzed in a manner similar to that of event-free survival.

Remission duration

Remission duration will be summarized by treatment group. Kaplan-Meier plots of the relapse-free survival will be displayed without displaying hazard rates, associated confidence intervals and p-values. Expected duration of response will be calculated based on an exponential model if appropriate.

Note that for remission duration no formal comparison between different treatment arms will be done since remission duration is based on a non-randomised set and therefore possibly biased.

ECOG performance score

The proportion of patients with improved (decreased), and with unchanged, ECOG at end of treatment with respect to baseline will be tabulated.

BI 6727 plasma concentration

See section [7.7.5](#)

Incidence and intensity of adverse events graded according to CTCAE

See section [7.7](#)

Pharmacodynamic monitoring

Analysis of pharmacodynamics will be performed separately and will not be contained in the CTR.

Pharmacogenetics

Analysis of pharmacogenetics will be performed separately and will not be included in the CTR.

7.6 EXTENT OF EXPOSURE

Standard descriptive analysis is planned for overall courses/visits by treatment groups.

7.7 SAFETY ANALYSIS

All safety analyses will be performed on the treated sets (separately for phase I and phase II).

7.7.1 Adverse events

The analyses of adverse events will be descriptive in nature and will be based on BI standards (see [\[3.1\]](#)). Adverse events will be coded with the most recent version of MedDRA. According to the BI standards, multiple occurrences of adverse events are collapsed to episodes if time overlapping or adjacent (maximal one day) on the MedDRA lowest level term and multiple episodes will be condensed to records on the preferred term and SOC level.

AEs as well as DLTs will be evaluated both for all courses as well as for first course only (in the phase I part).

The analysis of adverse events will be based on the concept of treatment emergent adverse events. Adverse events will be distinguished for the period in which the subjects are under study drug (on-treatment) as well as for screening, and post-study (For details on the analysing treatment period, see section [6.1.3](#)). If applicable, the actual dosage of BI 6727 administered on the day each adverse event starts will also be derived and will be included in the listing. The system organ classes will be sorted according to the standard sort order specified by EMEA, PTs will be sorted alphabetically (within SOC).

All patients will be reported in the summary tables under the initial treatment group (randomised treatment) including the initial treatment schedule.

AEs with onset date at Screening- and Post-study-period (as defined in [Table 6.1.1: 1](#)) will be displayed in two separate listings. Listings of screening events will not be sorted by initial treatment ([Table 6.1.2: 1](#)). But post-study listings will be sorted by initial treatment.

AE flags and attributes

An AE flag will be defined for patients who developed an AE that was CTCAE grade ≥ 3 , DLT, or serious AE.

An AE attribute "CTCAE grade 3/4 or 5 combined with drug relation" will be derived to avoid incorrect condensing. Consider, for instance, a patient with coincident drug-related abdominal pain with CTCAE 1, and non-related vomiting with CTCAE 3. Without the new attribute these AEs would be reported as drug-related Grade 3/4 under the SOC Gastrointestinal disorder. With the new AE attribute these AE would not be reported under that category.

The number of patients with DLT will be listed per treatment group with the respective events fulfilling the criteria for DLT.

A separate listing for all patients who developed AEs with CTCAE grade ≥ 3 , DLT, and serious AEs will be generated.

Incidence and intensity of adverse events

The overall incidence and intensity of adverse events, as well as relatedness of adverse events to treatment with BI 6727 will be reported for all treatment schedule arms.

Serious adverse events will be tabulated. In addition, Events leading to dose reduction or treatment discontinuation will be examined, but may not be reported as individual tables, depending upon the extent of overlap with the occurrence of DLT.

For the phase I part only, the dose-toxicity relationship will be examined descriptively and inferentially, using DLTs in treatment course 1 and DLTs up to the end of the on treatment phase, in separate analyses. Further, the time to first DLT will be explored descriptively in all dose groups, and Kaplan-Meier plots based upon the MTD group will be presented.

As a first step, for each time period, the number of DLTs that a patient has will be summarised. If the majority of the patients have either 0 or 1 DLT, then a simple logistic regression will be calculated. If however, there are quite a few patients with >1 DLT, then a proportional odds model will be used.

With this logistic regression, a model including only the BI 6727 dose (and intercept) will be used. Hence, by back-transformation of the logit model, the probability (and 95% confidence interval) of a DLT in this time period will be presented on a graph together with the dose. The dose corresponding to a 25% probability of a DLT in the time period will be indicated and the p-values for the intercept and slope of this model will also be included in the footnote. Additionally the expected toxicity level for the dose chosen in phase II will be provided.

Finally, the time on treatment prior to the first DLT will be presented graphically together with the dose. Different symbols will be used for patients with (filled dot) and without (unfilled dot) a DLT. Using the MTD group, the Kaplan Meier plot estimating the probability of an event over time will be presented.

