Duration of treatment: Minimum of one 28-day treatment cycle. Patients are eligible for repeated cycles until progression of disease and as long as neither patient nor investigator requests treatment discontinuation.		
Criteria for efficacy, pharmacokinetics and pharmacodynamics: Response, event free survival, relapse free survival, remission duration, overall survival, pharmacokinetics of trial drugs, pharmacodynamic monitoring (biomarker analysis for target inhibition, i.e. FACS analysis for cell cycle arrest, immunocytochemistry).		
Criteria for safety: Maximum tolerated dose, incidence and intensity of adverse events graded according to the common terminology criteria for adverse events (CTCAE, version 3.0), incidence of dose limiting toxicity, laboratory parameters.		
Statistical methods: Exploratory data analyses, conditional power evaluation		

**FLOW CHART FOR TREATMENT SCHEDULE A
BI 6727 + CYTARABINE (PHASE I AND IIA PART OF THE TRIAL)**

Trial Periods	Screen	Treatment							EoT	FU
Cycle *		! 1								
Visit	Screen	1	2	3	4	5	6	7**		
Days	-14 to -1	1 $\forall 1$	5 $\forall 2$	10	15	19 $\forall 2$	23	28 +3		
Informed consent	x									
Demographics	x									
Medical history	x									
Review of in-/exclusion criteria	x	x ^a								
Document ineligibility for intensive treatment	x									
12 lead-ECG (digital, triplicate)	x	x ^b		x ^c				x		
Blood for pharmacogenetics	x ^d									
Physical examination	x						x	x		
ECOG score, weight	x	x					x	x	x	
Height	x									
Vital signs	x	x ^e	x	x	x ^e	x	x	x		
Assignment / Randomisation	x ^f									
Adverse events		x	x	x	x	x	x	x	x	x
Concomitant therapy	x	x	x	x	x	x	x	x		
Administration of BI 6727		x		x						
Administration of cytarabine ^g		x	x	x						
Cytarabine compliance check			x	x	x					
Safety laboratory, incl. urinalysis	x ^h	x ^h	x	x	x ^h	x	x	x ^h		
Serum pregnancy test ⁱ	x						x			
Blood for pharmacokinetics ^k		x	x	x	x			x		
Disease assessment (blood, clinical)	x	x	x	x	x	x	x	x		
Bone marrow aspiration	x ^m	x ⁿ					x ^p			
Eligibility for further cycle							x			
Outcome (remission, progression, death)								x	x	
Other anti-leukaemia therapy									x	
Conclusion of patient participation								x		

EoT end of treatment

FU follow-up

* the visit number follows the cycle number, i.e. visit 2 cycle 1 will read C1_V2 and visit 2 cycle 2 will read C2_V2 and so forth

** can be the same day as visit one of the next cycle. Can be up to 3 days later, but must not be earlier than day 28

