7.3.3 Safety analyses

The occurrence of dose limiting toxicity (DLT) as well as the incidence and intensity of adverse events graded according to CTCAE, laboratory parameters, vital signs and duration of neutropenia will be evaluated.

All patients of the full analysis set (both phase I and phase II) will be included in the safety analyses.

Two analyses will be performed. The first analysis of safety will be performed for the first part of the trial (determination of the MTD, first cycle only, treatment regime=initial dose at the start of the treatment, full analysis set (phase I only)). This descriptive analysis will evaluate the MTD for each treatment schedule. The second analysis will be performed with

respect to all cycles and will act as a support for the determination of the MTD (full analysis set (both phase I and phase II)).

Incidence and intensity of adverse events

The severity, and timing of adverse events will indicate how well the treatment regimen is tolerated. Toxicities will be evaluated using the CTCAE grading scheme.

The overall incidence and intensity of adverse events, as well as relatedness of adverse events to treatment with BI 6727 monotherapy and in combination with cytarabine, respectively, will be reported for all treatment schedules.

Serious adverse events will be tabulated. In addition, events leading to dose reduction or treatment discontinuation will be examined, but may not be reported as individual tables, depending upon the extent of overlap with the occurrence of DLT.

Descriptive statistics will be used to describe changes in laboratory tests over time. In addition, all abnormalities of potential clinical relevance will be reported.

Events that started within the period starting with first administration of the trial drug and ending six weeks after the first treatment administration in the last treatment cycle will be considered as having occurred during treatment. In general, later events will be attributed to the post-study period and will be presented separately. However, post-study events will be examined to determine whether they need to be combined with on-treatment events in an additional table.

ECG measurements

Prolongation of QT/QTc times will be analysed descriptively and exploratory based on the ECG measurements described in [Section 5.2.7](#). Further details of the analysis of ECG data will be specified in the statistical analysis plan.

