5.3.2 Extent of exposure

Number of days of administration BI6727 [N]: Cumulative number of days with an administration of BI 6727.

Number of days of administration Cytarabine [N]: Cumulative number of days with an administration of cytarabine.

Number of courses initiated [N]: course initiated means: the patients received at least one administration of BI 6727 or cytarabine in the initiated course.

Cumulative total dose BI6727 [mg] = Sum of doses (administered dose of BI 6727) calculated across all courses

Total dose BI 6727 [mg] within a course = Sum of doses (administered dose of BI 6727) calculated per treatment course

Similar variables (cumulative total dose) will also be derived for LD-Ara-C.

Total exposure time to the trial drug [days] = date of first administration to MINIMUM (date of last trial drug administration of the last course + 21 days, death date if death occurs earlier than 21 days) + 1 day

Total observation time [days] = (last visit date (including follow-up) - date of randomisation + 1 day). Date of last visit does not include visit dates from follow-up where 'lost to follow-up' = yes.

The following two characteristic apply to BI 6727 only:

Number of patients with at least one dose escalation will be counted. A patient is considered to have at least one dose escalation if a dose escalation occurred at least once with BI 6727.

[figure not shown]
Number of patients with at least one dose reduction will be counted. A patient is considered to have at least one dose reduction if a dose reduction occurred at least once with BI 6727.

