300+Cy20	AG	Date of first administration of either BI 6727 300 mg d1 + 15 or Cytarabine 20 mg d1-10	Time of first administration of either BI 6727 300 mg d1 + 15 or Cytarabine 20 mg d1-10
350+Cy20	AI	Date of first administration of either BI 6727 350 mg d1 + 15 or Cytarabine 20 mg d1-10	Time of first administration of either BI 6727 350 mg d1 + 15 or Cytarabine 20 mg d1-10
400+Cy20	AK	Date of first administration of either BI 6727 400 mg d1 + 15 or Cytarabine 20 mg d1-10	Time of first administration of either BI 6727 400 mg d1 + 15 or Cytarabine 20 mg d1-10
Cy20	W	Date of first injection of Cytarabine 20 mg d1-d10	Time of first injection of Cytarabine 20 mg d1-d10

Short label (REGSHNM in E_REG) unblinded	Sort order (SORTREG in E_REG)	Start date (CRF)	Start time (CRF/ derived)
Post-trt	X	For BI 6727 monotherapy: Date of last administration	For BI 6727 monotherapy: Stop time of last administration + 1min.
		For BI 6727 combi with Cytarabine or Cytarabine mono: Date of last administration of BI 6727 or Cytarabine whichever is later	For BI 6727 combi with Cytarabine or Cytarabine mono: Time of last administration + 1min.
Post-study	Y	Date of last administration of trial medication (last treatment course) + 21 days.	0:00:00

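### Phase II adverse events are summarised by arm only as crude all-course incidence, which can mislead as a measure of relative toxicity if treatment duration differs between arms

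*SAP*

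**What the plan says.** **Which analysis covers which phase.** SAP 7.7.1: "AEs as well as DLTs will be evaluated both for all courses as well as for first course only (in the phase I part"). Protocol 7.3.3 plans two safety analyses. The first is described as "determination of the MTD, first cycle only, treatment regime=initial dose at the start of the treatment, full analysis set (phase I only")). The second has this scope: "respect to all cycles and will act as a support for the determination of the MTD (full analysis set (both phase I and phase II")). Phase II patients enter only the second.

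**What is tabulated.** SAP 5.2.6 condenses each patient's episodes to one worst-case record per preferred term. SAP 7.7.1 then reports incidence and intensity by initial treatment group. It calls these analyses descriptive.

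**How long patients are at risk.** The protocol synopsis sets no fixed duration: "Patients are eligible for repeated cycles until progression of disease and as long as neither patient nor investigator requests treatment discontinuation". In SAP Table 6.1.1: 1 the post-study period begins at "Date of last administration of trial medication (last treatment course) + 21 days", which closes the on-treatment window. Protocol 5.2.1 also uses 21 days after the last dose. Protocol 7.3.3 uses a different limit: events from first dose and "ending six weeks after the first treatment administration in the last treatment cycle will be considered as having occurred during treatment".

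**What is already derived.** SAP 5.3.2 defines "Total exposure time to the trial drug [days] = date of first administration to MINIMUM" of last dose plus 21 days and death. SAP 7.6 describes exposure by treatment group. Neither document uses it as a denominator for AEs. SAP Table 6.1.3: 1 defines a Course 1 analysis period without naming a phase, but no text applies it to phase II AEs. The time-to-first-DLT and dose-toxicity analyses in SAP 7.7.1 are for phase I only.

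**The concern.** The share of patients with at least one event, and each patient's worst grade, can only rise as the observation window lengthens. When the window ends with treatment, and treatment ends at progression, the window length is itself an outcome of treatment. Two arms with the same risk per month will then show different incidences if one stays on treatment longer.

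This matters because combination versus LD-Ara-C in phase II is the trial's only randomised look at what BI 6727 adds in toxicity. AE incidence and intensity is the first secondary endpoint in protocol 2.3. Protocol 1.4 notes that the two drugs' toxicities overlap, and protocol 3.1 says the results should inform further development. The sample size assumption of 30% versus 15% response (protocol 7.6.2) makes longer treatment in schedule A plausible. It could equally be shorter if toxicity ends treatment early.

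**Working it through.** **1. The plan's own figures.** Neither document gives an AE rate or an expected treatment duration, so there is no safety figure to reproduce. The one design figure for the randomised comparison is the response power in protocol 7.6.2: 43 per arm, 15% versus 30%, one-sided type I error 18.9%, power 78.3%. With pooled variance, SE = sqrt(2 × 0.225 × 0.775 / 43) = 0.09006 and 0.15 / 0.09006 = 1.666. Subtracting the critical value 0.882 gives 0.784, and Φ(0.784) = 78.3%. This agrees, and nothing below depends on it.

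**2. Equal risk, unequal exposure (illustration).** Assume the same constant risk r per month in both arms and mean exposure m months.
- If every patient has exactly m months: incidence = 1 − exp(−r m).
- If exposure is exponential with mean m: incidence = r m / (1 + r m).

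| r per month | m, longer vs shorter arm | Fixed exposure | Gap (points) | Exponential exposure | Gap (points) |
|---|---|---|---|---|---|
| 0.2 | 4 vs 2 | 55.1% vs 33.0% | 22 | 44.4% vs 28.6% | 16 |
| 0.2 | 3 vs 2 | 45.1% vs 33.0% | 12 | 37.5% vs 28.6% | 9 |
| 0.1 | 4 vs 2 | 33.0% vs 18.1% | 15 | 28.6% vs 16.7% | 12 |
| 0.1 | 3 vs 2 | 25.9% vs 18.1% | 8 | 23.1% vs 16.7% | 6 |

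The true difference is zero in every row. Exposure that ends at progression varies between patients, so the exponential columns are the more realistic of the two. If the control arm is treated longer, each gap changes sign. With equal exposure it vanishes.

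**3. The same check by cycle.** With risk p per cycle over k cycles, incidence = 1 − (1 − p)^k. For 2 cycles (C) versus 4 (A), p = 10%, 20% and 30% give 19.0% vs 34.4%, 36.0% vs 59.0% and 51.0% vs 76.0%, so 15 to 25 points. For 3 cycles (C) versus 2 (A) the gap is −8 to −15 points. These figures treat cycle counts as fixed.

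**4. Window length from the documents' own schedule.** The last scheduled dose in a cycle is day 15 in schedule A and day 10 in schedule C.
- SAP rule, one completed cycle: post-study starts on day 15 + 21 = 36 in A and day 10 + 21 = 31 in C. On-treatment is therefore days 1-35 versus days 1-30.
- Effect of those five days alone, at p = 20% per 28 days: 1 − 0.8^(35/28) = 24.3% versus 1 − 0.8^(30/28) = 21.3%.
- Protocol 7.3.3 rule: six weeks after day 1 of the last cycle, day 1 + 42 = 43, the same in both arms.

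**5. The Course 1 period in SAP Table 6.1.3: 1.** It ends at the start of course 2 or at post-study. Without a course 2 it is days 1-35 in A and days 1-30 in C. Where course 2 waits for count recovery (up to three weeks, protocol 4.1.4), it can reach about 28 + 21 = 49 days. It is not an equal-length window.

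**6. What the alternatives return under step 2.** At r = 0.2 per month and the SAP's 30-day month, a common 28-day window gives 1 − exp(−0.2 × 28/30) = 17.0% in both arms. Events per patient-month give 0.2 in both arms.

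**The case against.** A reader might go further and conclude that the randomised safety comparison is biased. The documents do not support that. No formal AE comparison is planned: the analyses are descriptive, and the group comparisons in SAP 7.4.1 concern objective response. All-course incidence is a legitimate summary of total AE burden under each treatment strategy. Exposure, courses initiated and cumulative dose are reported by group, so an imbalance would be visible. Durations are unknown and the direction could go either way. All of this stands, and it limits the point to what the summary can suggest when read as relative toxicity. Seeing an exposure imbalance still does not tell the reader how much of an AE difference it explains.

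A reader might also infer that extending the Course 1 analysis to phase II would give an equal-length comparison. Step 5 shows that it would not.

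Rates per patient-month have their own weakness: they are fair only if the hazard is roughly constant. Suppose both arms have 0.2 events in the first month and 0.1 per month after that. Four months then gives (0.2 + 3 × 0.1)/4 = 0.125 per month and two months gives (0.2 + 0.1)/2 = 0.150, so the longer-treated arm looks safer with no true difference. This stands, and it is why a fixed early window is needed beside any rate.

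Finally, the sponsor's AE standards and SAP section 9 are cited but were not in the text reviewed, so a further display there cannot be excluded.

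**Conclusion.** The point holds as a limitation of the planned summary. For phase II, the visible plan offers only crude all-course incidence and worst grade. The first-course view is confined to phase I, and the exposure time already derived is described but not used. Read as relative toxicity, the result can mislead in either direction.

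The size depends wholly on assumptions. For equal risk of 0.2 per month and mean exposure of 4 versus 2 months, it is about 16 points with exponential exposure and 22 with fixed exposure. Over the other scenarios in the table it runs from 6 to 15 points, and it is zero if exposure is equal. One asymmetry needs no assumption about duration: under the SAP rule, schedule A is scheduled to have five more counted days than schedule C for the same number of cycles. This is an inexpensive improvement to descriptive tables and does not make the planned tables invalid.

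**What to change.** In SAP 7.7.1, with a matching change in protocol 7.3.3, keep the all-course tables and add for the two randomised phase II arms:

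- **(a)** AE incidence and worst grade over a common fixed window from first dose, for example days 1-28, counting events whether or not dosing has stopped. Protocol 5.2.1 already requires reporting of events up to six weeks after the last dose, so the data will exist. Use this window in place of the Course 1 period as now defined.
- **(b)** Events per patient-month of total exposure time, or time to first event, for all AEs, grade 3 or higher AEs, serious AEs and infections. Add a note that rates assume a roughly constant hazard.

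State in SAP Table 6.1.3: 1 which phase the Course 1 analysis covers. Reconcile the on-treatment AE windows: last dose plus 21 days (protocol 5.2.1, SAP Table 6.1.1: 1) against six weeks after the first dose of the last cycle (protocol 7.3.3). The numerator and denominator of any rate must follow the same rule.

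The cost is a few extra tables from variables already derived, and a caveat on the rates.

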4.1.3 Selection of doses in the trial

Two treatment schedules will be investigated in the phase I part of the trial to determine the MTD. All patients will receive either BI 6727 on days 1 and 15 either as monotherapy or in combination with LD-Ara-C (2 x 20 mg/d on days 1-10) in 28-day cycles. The starting dose of BI 6727 in treatment schedule A is 150 mg and corresponds to 50 % of the recommended Phase II dose of 300mg and 38% of the MTD of 400mg that has been determined in a phase I monotherapy dose escalation trial to be well tolerated.

To determine the MTD (for definition see 5.2.4), dose escalation for BI 6727 will be conducted following the “3 + 3 design with de-escalation” ([R04-0569](#)). A cohort of three patients will be treated at the starting dose level and observed until the end of the cycle. The dose level will be escalated with each new cohort until at least one out of three patients of a cohort experiences DLT (for definition see [section 5.2.3](#)). If one patient experiences a DLT, then three additional patients will be treated at the same dose level; if none of the three additional patients experiences a DLT, then the dose escalation will be continued by treating the next cohort of three patients at the next higher dose level. If at least two out of up to six patients at a dose level experience a DLT, the MTD has been exceeded and the dose will be deescalated until a dose level is reached in which at most one DLT out of six patients is observed ([R01-0028](#)). A dose step for escalation shall not exceed 50 mg/administration, a dose step for de-escalation shall not exceed 50 mg/administration.

The starting of BI 6727 for dose escalation in schedule B will be the dose determined as BI 6727 MTD in schedule A.

The dose of the trial drug on days one and fifteen will always remain the same (i.e. simultaneous and equal dose escalation for days one and fifteen). The dose of cytarabine remains always unchanged.

In case two or more cases of DLT are observed at the starting dose of 150 mg either in monotherapy or in combination with LD-Ara-C the dose BI 6727 will be deescalated to a lower dose cohort as outlined above.

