7.3.1 Primary analyses

7.3.1.1 Assessment of the MTD and derived variables for first cycle only

One primary objective for this study is the tolerability and safety of BI 6727 as monotherapy and in combination with cytarabine, respectively, as reflected by the MTD (for definition of MTD please refer to [5.2.4](#)).

In addition, to determine the MTD, an analysis on conditional probabilities for a DLT given the dose will be done, based on the logistic regression model.

For the analysis of the tolerability and safety, please refer to [section 7.3.3](#).

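### SAP 7.7.1 states no rule for separated DLT data, although course-1 data from a bare 3+3 of about 21 patients, analysed per schedule, would give no finite logistic fit in roughly 30–45% of trials

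*SAP*

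**What the plan says.** Protocol 7.3.1.1, under the primary analyses, adds a model to the rule-based MTD: "an analysis on conditional probabilities for a DLT given the dose will be done, based on the logistic regression model".

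SAP 7.7.1 (incidence and intensity of adverse events) gives the detail, for phase I only:

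- The choice of model depends on the data: "If the majority of the patients have either 0 or 1 DLT, then a simple logistic regression will be calculated". If a sizeable but unquantified number of patients have more than one DLT, a proportional odds model is used instead.
- The covariates are minimal: "a model including only the BI 6727 dose (and intercept) will be used".
- Two periods are modelled, "using DLTs in treatment course 1 and DLTs up to the end of the on treatment phase, in separate analyses".
- The outputs are a DLT probability curve with 95% confidence interval, p-values for intercept and slope, the expected toxicity at the phase II dose, and a target dose: "The dose corresponding to a 25% probability of a DLT in the time period will be indicated".

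Neither section names an estimator or an interval type, says what to do if the fit does not converge, or says whether schedules A and B are modelled separately.

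**The concern.** A 3+3 escalation ends at the first tier with two DLTs, and every tier it passed has at most one DLT in six patients. Two ordinary outcomes therefore leave the likelihood without a maximum: no DLT below the top tier, or a DLT in every top-tier patient with all other DLTs in the tier just below. In both, some dose cleanly divides patients with a DLT from those without, apart from ties at that dose. The fitted slope then grows without limit. Software still prints a slope, a standard error, a p-value and a 25% dose, but these depend on when the iteration stopped.

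At stake are the reported 25%-DLT dose, its interval and the expected toxicity at the phase II dose.

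**Working it through.** **1. The plan's own figures.** Protocol 7.6.1 tabulates the chance of two or more DLTs in six patients, P = 1 − (1−p)^6 − 6p(1−p)^5. For p = 0.40, 0.42 and 0.45 this gives 0.7667, 0.7965 and 0.8364, matching the stated 0.77, 0.80 and 0.84. The size of 21 per schedule is (5 + 2) × 3. The documents give no non-convergence rate to reproduce.

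**2. What separation does.** Take 0/3, 0/3, 0/3, 0/6 and 2/3 DLTs at 150, 200, 250, 300 and 350 mg. The log-likelihood approaches 2 ln(2/3) + ln(1/3) = −1.91 as the slope b (per 50 mg) grows, and never reaches it. The fitted logit at 350 mg tends to ln 2, and logit(0.25) = −ln 3, so

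25% dose ≈ 350 − 50 × (ln 2 + ln 3)/b = 350 − 89.6/b mg.

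| Iterations | Slope b | SE | Wald p | 25% dose, formula | 25% dose, fitted |
|---|---|---|---|---|---|
| 8 | 7.83 | 8.9 | 0.378 | 338.6 | 339 |
| 15 | 14.83 | 291.1 | 0.959 | 344.0 | 344 |
| 25 | 24.83 | 43,196 | 1.000 | 346.4 | 346 |

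The 25% dose drifts to the top dose tested. With 1/6 at 300 mg and 3/3 at 350 mg the fit also diverges. There the logit at 300 mg tends to −ln 5, and the 25% dose is about 300 + 50 × (ln 5 − ln 3)/b = 300 + 25.5/b mg. That is 303, 302 and 301 mg at b = 8.58, 15.58 and 25.58, so it drifts to 300 mg. In both cases the grid sets the answer. With 1/6 and then 2/3 the fit is finite: slope 2.50, SE 1.5, p = 0.089, 25% dose 313 mg.

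**3. How often.** Inputs from Protocol 4.1.3: "The starting dose of BI 6727 in treatment schedule A is 150 mg"; "A dose step for escalation shall not exceed 50 mg/administration" (50 mg used); "If at least two out of up to six patients at a dose level experience a DLT, the MTD has been exceeded". Six patients are treated at the MTD (Protocol 5.2.4). The documents give no DLT rates by dose, so logit-linear curves were assumed. A trial counts as having no finite fit if the lowest dose with a DLT is at or above the highest dose with a DLT-free patient (or the reverse), if there is no DLT, or if only one dose was used. Selected curves, 10,000 trials each, one schedule:

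| P(DLT) at 150 mg | at 400 mg | Bare 3+3 | Topped up at MTD to 32 | Topped up at MTD to 56 |
|---|---|---|---|---|
| 0.01 | 0.30 | 45.2% | 26.5% | 18.9% |
| 0.02 | 0.45 | 36.6% | 13.3% | 7.5% |
| 0.05 | 0.40 | 34.2% | 9.9% | 5.2% |
| 0.05 | 0.50 | 34.6% | 9.3% | 4.6% |
| 0.10 | 0.40 | 32.5% | 5.6% | 2.8% |
| 0.01 | 0.70 | 42.2% | 16.2% | 9.7% |

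Over all 12 curves, the bare 3+3 gives 32–45% (mean 37%), 32 patients give 6–26% (mean 13%), and 56 give 3–19% (mean 8%). A second set of nine curves (25%-DLT dose 300, 350 or 400 mg; slope 0.5, 0.8 or 1.2 per 50 mg) gives 30–45% for the bare 3+3, with mean size 18–25.

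**4. Other data sets.**

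- One-dose trials left out: still about 27–44%.
- Schedule B plus 15 extension patients at the MTD: 14–23%, with 33% in one scenario made up mostly of one-dose trials.
- Schedules A and B pooled on dose: 2.0–3.2% separated. A further 0.4–10% of those runs found no schedule A MTD, so schedule B never started.

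**The case against.** The strongest reply is that the bare 3+3 is not the data set to be analysed. Protocol 7.6.1 says its 21 leaves out additional patients at the presumptive MTD. Schedule B may gain 15 (Protocol 3.1 and 4.1.3). The synopsis now shows 32 and 56 phase I patients, which with 44 and 45 in phase II sum to its total of 177. SAP 6.3 counts every treated phase I patient. This stands, and a reader who carried a one-third failure rate over to the whole of phase I would go beyond the documents. The lower rates have a condition of their own: they put all extra patients at the MTD. If the extra patients were DLT-free replacements, assuming 30% replacement, the rate was 29–41% at mean sizes of 24–32. If they came only from more escalation cohorts, it was 0–14%.

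Pooling nearly removes the problem. However, no text plans it, and it would mix combination and monotherapy although SAP 5.1.1 calls for two separate MTDs. Nor can schedule B be relied on for the safety analysis of Protocol 7.3.4, because its escalation starts only after schedule A's MTD is known.

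Four further points stand:

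- Maximum likelihood and Wald intervals are the usual reading of the text, not its words.
- The all-course analysis was not simulated. Longer follow-up can add DLTs at lower tiers, so the course-1 rate does not carry over.
- SAP section 9, cited for the phase I safety update, is not in the text available. The supportable statement is that 7.7.1 gives no rule, not that none exists.
- A proportional odds model still yields the probability of at least one DLT, so the switch need not change the quantity estimated. Its two triggers do overlap, lack a threshold and depend on the data, and the switch does not cure separation.

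**Conclusion.** The point holds in a limited form. A plain logistic regression of DLT on dose, with no stated rule for separation, is a poor match to 3+3 data. For course-1 data from a bare 3+3 of about 21 patients, analysed per schedule, the share of trials with no finite fit is about 30–45%. With extra patients at the MTD it is roughly 3–26%, apart from the single 33% scenario above, and with pooling about 2–3%. All of these rest on assumed dose-toxicity curves and on maximum likelihood.

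A reader might infer that the regression outputs will be unusable, or that the MTD is at risk. The documents support neither. In most simulated trials the fit is finite, though it can be imprecise, and divergence shows itself in the standard error. The MTD comes from a DLT count (Protocol 5.2.4, SAP 5.1.1). The phase II dose rests on the MTD and on safety over all cycles (Protocol 7.3.4). All analyses are exploratory (SAP 3.3), and no decision rule uses the 25%-DLT dose. What is exposed is the reported dose-toxicity summary, which should be corrected because the failure is predictable and cheap to avoid.

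**What to change.** Change SAP 7.7.1 as follows:

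- For both time periods, fit a Firth-penalised logistic regression, or a Bayesian one with a stated weak prior, to the patient-level outcome of at least one DLT. Take the interval for the curve and for the 25%-DLT dose from the profile likelihood or the posterior.
- Use that binary outcome as the main model whatever the number of DLTs per patient. Keep any proportional odds model as supplementary only.
- State that schedules A and B are modelled separately, and whether schedule B extension patients enter.

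The cost is SAP wording and a standard software option, with no new data. The downside is slight shrinkage of the slope.
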